## 4 STUDY ENROLLMENT AND WITHDRAWAL

### 4.1 Participant Inclusion Criteria

A participant must meet all of the following inclusion criteria to be eligible for initial enrollment and randomization:

- 1) Provides a signed and dated informed consent form
- 2) Is between 18 and 65 years of age (inclusive; male or female and any race or ethnicity)
- 3) Meets diagnostic criteria for TMD, Group II: Masticatory Muscle Disorders, 1A: Myalgia
- 4) Has experienced facial pain for at least 3 months
- 5) Has experienced facial pain for at least 10 days of the last 30 days
- 6) At Screening and Baseline Visit (Visit 0), reports an average pain intensity rating over the past week of  $\geq 30$  on a numerical rating scale (0-100)
- 7) At randomization (Visit 1), has satisfactorily completed at least 4 entries per week in the Daily Symptom Diary within the preceding week and reported an average pain intensity score  $\geq 30$  on a numerical rating scale (0-100) or reports a rating of average daily pain intensity of  $\geq 30$  on the same scale on at least 3 days over the past week
- 8) If taking a prescription medication (with the exception of prescription formulations of NSAIDs, acetaminophen, and aspirin) episodically (or as needed) for the management of pain, agrees to discontinue its use prior to or at the Screening and Baseline Visit
- 9) If taking a prescription medication daily for the management of pain, agrees to continue the daily use of the medication throughout the study
- 10) If taking an over-the-counter pain medication daily, agrees to continue the daily use of the medication throughout the study
- 11) Agrees to not commence any new prescription medication for the management of pain throughout the study
- 12) Agrees to not commence any injection therapy for pain (e.g., tender or trigger point injections, steroid injections) during the course of the study
- 13) Agrees to not use acupuncture, biofeedback, or transcutaneous electrical nerve stimulation (TENS) for the management of pain during the course of the study
- 14) Agrees to not commence occlusal splint therapy during the course of the study
- 15) Agrees to continue use of splint therapy if commenced more than 30 days previously

---

- 16) Females agree to limit consumption of alcohol to no more than 7 drinks\* and males agree to limit consumption of alcohol to no more than 14 drinks\* a week for the duration of the study
- 17) Females of childbearing potential, agrees to use one of the following methods of contraception throughout the study: licensed hormonal method, intrauterine device, condoms with contraceptive foam, abstinence, or vasectomy in partner (if post-menopausal, must not have menstruated for at least 12 consecutive months)
- 18) Willing and able to understand and comply with all study procedures and be available for the duration of the study

## 4.2 Participant Exclusion Criteria

A potential participant who meets any of the following criteria will be excluded from enrollment and randomization:

- 1) Has a history of congestive heart failure or the presence of any of the following cardiovascular conditions: clinically significant abnormal 12-lead ECG, sinus bradycardia (resting heart rate below 55 beats per minute although lower heart rates will be acceptable upon the review and approval by the site cardiologist), greater than first degree heart block, coronary artery disease, uncontrolled hypertension, or hypotension (systolic blood pressure below 90 mm Hg). In individuals with a heart rate below 55 beats per minute, the site cardiologist will review the participant's medical history, including any concomitant medications, to ensure that they are in good general health and have no medical contraindications to taking propranolol.
- 2) Has any of the following medical conditions: bronchial asthma, nonallergic bronchospasm (chronic obstructive pulmonary disease and emphysema), renal failure or dialysis, diabetes mellitus, hyperthyroidism, fibromyalgia, or uncontrolled seizures
- 3) Has known hypersensitivity to propranolol or components of the placebo capsules
- 4) Currently taking a  $\beta$ -blocker or medication that may interact with propranolol, including haloperidol, intravenous verapamil, and catecholamine-depleting drugs, such as reserpine, within 30 days prior to the Screening and Baseline Visit
- 5) Currently taking an opioid medication, whether episodically or daily, within 30 days prior to the Screening and Baseline Visit
- 6) Has commenced a new daily prescription medication for the management of pain within 30 days prior to the Screening and Baseline Visit

---

\* one standard drink is defined as 12 ounces of regular beer, 5 ounces of wine, or 1.5 ounces of 80 proof distilled spirits.

---

- 7) Used any injection therapy (e.g., tender or trigger point injections, steroid injections) for the management of pain within 2 weeks prior to the Screening and Baseline Visit
- 8) Used acupuncture, biofeedback, or TENS for the management of pain within 2 weeks prior to the Screening and Baseline Visit
- 9) Has commenced occlusal splint therapy for the management of facial pain within 30 days prior to the Screening and Baseline Visit
- 10) Has experienced facial trauma or orofacial surgery within 6 weeks prior to the Screening and Baseline Visit
- 11) Is undergoing current active orthodontic treatment (passive retainers are permitted)
- 12) Has a history of major depression or other major psychiatric disorder requiring hospitalization within the last 6 months prior to the Screening and Baseline Visit
- 13) Has a history of treatment for drug or alcohol abuse within the last year
- 14) Has scored 8 or more on the Alcohol Use Disorders Identification Test (AUDIT) at the Screening and Baseline Visit
- 15) Currently smokes at least 25 cigarettes per day
- 16) Currently being treated with chemotherapy or radiation therapy
- 17) Has been treated with another investigational drug or treatment within 30 days prior to the Screening and Baseline Visit
- 18) Is pregnant or nursing
- 19) Anything that, in the opinion of the investigator, would place the participant at increased risk or preclude the participant's full compliance with or completion of the study

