#### **5.7.1.1 Over-the-counter medications**

NSAIDs are most often used to manage pain in TMD patients. If a participant is taking an over-the-counter medication daily for pain management, the participant will be encouraged to continue the same usage of that medication throughout the study. The usage of short-acting, non-prescription analgesics (e.g., NSAIDs, aspirin, and/or acetaminophen) by participants during the study will be recorded and quantified at each visit, and the usage will be classified as either daily or episodic.

---

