### **5.8 Protocol Deviations Related to the Use of Investigational Product and Concomitant Therapies**

The following protocol deviations related to the use of investigational product and concomitant therapies will be considered major protocol deviations and reported on a case report form in the EDC system.

- Participant is unable to reach the maintenance dosage of the study drug or placebo or is unable to remain on the maintenance dosage.
- Initiation of opioid medications.
- Initiation of TMJ surgical treatment (including TMJ arthrocentesis).
- Initiation of therapeutic injections for the management of pain.
- Initiation of occlusal splint therapy.
- Initiation of any of the following nonpharmacological therapies: acupuncture, biofeedback, and/or TENS.
- Initiation after Visit 1 and usage of short-acting, non-prescription analgesics (e.g., NSAIDs, aspirin, and/or acetaminophen) for pain that exceeds the definition of episodic use as described in Section 5.7.1.

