### Calcium Channel Blockers

Caution should be exercised when patients receiving a beta-blocker are administered a calcium-channel-blocking drug with negative inotropic and/or chronotropic effects. Both agents may depress myocardial contractility or atrioventricular conduction.

There have been reports of significant bradycardia, heart failure, and cardiovascular collapse with concurrent use of verapamil and beta-blockers.

Co-administration of propranolol and diltiazem in patients with cardiac disease has been associated with bradycardia, hypotension, high degree heart block, and heart failure.

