#### **Non-Cardiovascular Drugs**

##### Nonsteroidal Anti-Inflammatory Drugs

Nonsteroidal anti-inflammatory drugs (NSAIDs) have been reported to blunt the antihypertensive effect of beta-adrenoreceptor blocking agents.

Administration of indomethacin with propranolol may reduce the efficacy of propranolol in reducing blood pressure and heart rate.

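### Exclusion 4 (beta-blockers and interacting drugs) has no counterpart among the major deviations, so a placebo participant who starts a beta-blocker after randomization for a non-pain reason stays in the per-protocol control group

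*Protocol*

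**What the plan says.** Exclusion 4 in Protocol 4.2 bars current users of a beta-blocker and of any "medication that may interact with propranolol, including haloperidol, intravenous verapamil, and catecholamine-depleting drugs, such as reserpine, within 30 days prior to" Visit 0. The sentence that introduces the exclusion list sets its scope: "A potential participant who meets any of the following criteria will be excluded from enrollment and randomization".

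For the time after entry, the rule on new prescription drugs is Inclusion 11: "Agrees to not commence any new prescription medication for the management of pain throughout the study". Protocol 5.7 has other medications recorded, and it gives no list of prohibited non-pain drugs.

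Protocol 5.8 then names seven events that "will be considered major protocol deviations and reported on a case report form in the EDC system": failure to reach or stay on the maintenance dosage; starting opioids; TMJ surgery; therapeutic injections; splint therapy; acupuncture, biofeedback or TENS; and non-prescription analgesic use beyond the episodic limit. SAP 5.2 has the same seven categories.

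The per-protocol sample (Protocol 11.3.2, SAP 4.2) drops assessments from the visit at which one of these seven is found, and drops all assessments of participants with study-drug compliance below 60%. It has no other exclusion.

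**The concern.** The test drug is a beta-blocker. The per-protocol comparison is meant to set participants who took it as planned against participants who took placebo without a co-treatment that blurs the contrast. The protocol applies that logic to pain treatments but not to the test drug's own class. A placebo participant given a beta-blocker for, say, blood pressure or palpitations would count as a clean control, and any pain benefit from that drug would pull the per-protocol difference toward zero.

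The comparison also has a role in the plan. SAP 8.3.1 uses agreement between the intention-to-treat and per-protocol results to decide whether all later analyses use the intention-to-treat population only.

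The same omission means that the documents do not say whether Exclusion 4 still applies once study drug has been started.

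**Working it through.** **Step 1. Set each co-treatment exclusion beside what follows it.**

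| Protocol 4.2 | On-study rule in Protocol 4.1 | Item in Protocol 5.8 and SAP 5.2 |
|---|---|---|
| 4: beta-blocker or interacting drug | none, unless newly prescribed for pain (Inclusion 11) | none |
| 5: opioids | Inclusion 11, if prescribed for pain | yes |
| 6: new daily prescription pain drug | Inclusion 11 | none, except opioids |
| 7: injections | Inclusion 12 | yes |
| 8: acupuncture, biofeedback, TENS | Inclusion 13 | yes |
| 9: splint | Inclusion 14 | yes |

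Exclusion 4 is the only row with neither a rule covering its non-pain use nor a deviation item.

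**Step 2. Trace one case.** A placebo participant starts a beta-blocker in week 3 for a non-pain reason and keeps taking the capsules.
- Protocol 14.12 defines a deviation as noncompliance with the protocol, GCP or the Manual of Procedures. No stated protocol rule is broken.
- None of the seven items in 5.8 applies, and compliance is above 60%.
- The Visit 3 and Visit 4 assessments therefore stay in the per-protocol sample as placebo.

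Had the same participant started an opioid or a splint, the assessments from the visit at which this was found would be dropped. The beta-blocker case leaves the sample only if the maintenance dosage is not kept (first item of 5.8), compliance falls below 60%, or another listed event occurs.

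**Step 3. Size.** Inputs from Protocol 11.2: baseline 3000, net change -810 on drug and -270 on placebo, SD 1190, 100 per arm.
- Planned difference: 810 - 270 = 540, which equals (27% - 9%) × 3000.
- Let f be the share of placebo participants who start a beta-blocker, and suppose that each gains the full drug effect. The difference becomes 540 × (1 - f).
- The documents give no value for f. Assuming 1 to 3%, the loss is 540 × 0.01 = 5.4 to 540 × 0.03 = 16.2 points, leaving 534.6 to 523.8.

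**Step 4. Power, for scale only.** The standard error is 1190 × √(2/100) = 168.3.
- The stated 94% power is not recovered from 540 with a two-sided 0.05 test: 540/168.3 = 3.209, and Φ(3.209 - 1.960) = 89.4%.
- It is recovered from the haplotype-weighted difference, 0.3 × 1080 + 0.5 × 540 + 0.2 × 0 = 594, which gives 94.2%. A one-sided test at 540 gives 94.1%.
- The present point does not depend on which was meant. On 594 the loss would be 5.9 to 17.8 points.
- On 540, two-sided, power goes from 89.4% at f = 0 to 88.8% at 1% and 88.2% at 2%. The per-protocol sample will have fewer than 100 per arm if any participants are excluded, so only the drop of about one point is informative.

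**The case against.** The strongest reply is that the plan is less bare than the deviation list suggests. Inclusion 11 covers a beta-blocker newly prescribed for pain, arguably including migraine prophylaxis. Not every on-study restriction concerns pain treatment: Inclusion 16 limits alcohol. Blood pressure and heart rate are taken at every clinic visit (Protocol 2.3.1), new clinically significant conditions are adverse events (8.4.4), the site dentist or cardiologist manages adverse events (8.1), the investigator may withdraw a participant (4.4.4), and an untolerated dosage leads to a recorded deviation (5.3). All of this stands. It limits the point to the lack of a specific rule and of a deviation item. It does not close the gap, because a breach of Inclusion 11 is not a 5.8 item either, and monitoring does not remove anyone from the per-protocol sample.

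The Manual of Procedures is not available and may contain a medication rule. It would not by itself change the list that defines the per-protocol sample.

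Three stronger readings are tempting, and the documents do not support them.
- A reader might infer that participants on two beta-blockers are left without oversight. The safeguards above are generic, but they exist.
- A reader might infer that Exclusion 4 contradicts the rest of the plan, because Appendix B says "Nonsteroidal anti-inflammatory drugs (NSAIDs) have been reported to blunt the antihypertensive effect of beta-adrenoreceptor blocking agents" while Protocol 5.7.1.1 says "NSAIDs are most often used to manage pain in TMD patients". But Inclusions 8 to 10 provide for continued analgesic use, with NSAIDs expressly excepted in Inclusion 8, and specific provisions govern a general clause. The insert describes a blunted antihypertensive effect, and hypertension is not what this trial treats.
- A reader might infer that only intravenous verapamil is excluded, although Appendix B warns without limit of route: "There have been reports of significant bradycardia, heart failure, and cardiovascular collapse with concurrent use of verapamil and beta-blockers". The word including in Exclusion 4 makes the named drugs examples, so other routes are not thereby admitted.

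**Conclusion.** The point holds as a gap in the definition of the per-protocol sample. It is not evidence that the primary result is at risk: the intention-to-treat sample keeps assessments after protocol violations by design, and its definition does not refer to the deviation list.

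The size rests on an assumed initiation rate of 1 to 3% in the placebo arm. For that rate, 5 to 16 of 540 points is an upper bound, for two reasons. It gives every starter the full propranolol effect, although Protocol 2.1.5 reports that in rats the COMT-related hyperalgesia was not blocked by beta-1 antagonists. It also ignores starters whose dosage changes and who leave the sample anyway.

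The case for acting is a clean control definition, consistency with how the plan treats Exclusions 5 and 7 to 9, and an explicit position on Exclusion 4 during treatment. It is worth correcting because the correction is cheap.

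**What to change.** Add to the major deviations in Protocol 5.8 and SAP 5.2: initiation after Visit 1 of a beta-blocker or other Exclusion 4 medication. Assessments from the visit at which it is found then leave the per-protocol sample under the existing rule. Visit 1 is the right trigger because eligibility is reviewed again there (Protocol 4.4.1 and 6.3.1). Classing the event this way for analysis need not settle clinical management: Protocol 5.3 already keeps participants on a reduced dosage in the study while recording a deviation.

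Report the number of such participants by arm. SAP 6 already summarizes concomitant medications by drug class but does not say by arm.

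Reconcile Protocol 4.2 with 4.4.4 and 5.7 so that they say whether Exclusion 4 continues to apply on treatment. The answer, and the drugs it covers, are for the investigators.

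Cost: one line in each document and a protocol clarification, made before database lock. If only the SAP is changed, SAP 11, which now states that there are no changes from the protocol, must record it. No new data are needed, since concomitant medications are recorded from Visit 0 through Visit 5. The downside is the loss of a few per-protocol assessments.

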### **4.3 Strategies for Recruitment and Retention**

Participants will be recruited from existing TMD patient registries and from various clinics at the three universities. Clinicians at these sites will be made aware of the study and asked to inform their patients of the study and to provide their patients with study contact information. In addition, participants may be recruited through print and electronic media advertisements. All recruitment materials will be submitted to the Institutional Review Boards (IRBs) for review and approval prior to their use.

Participants will be reminded of each upcoming visit by telephone, text message, email, or letter. Participants will be told about the importance of keeping each scheduled appointment, and they will be instructed to contact the study staff as soon as possible if they are unable to attend a scheduled appointment. Participants who miss a scheduled visit without notifying the study staff will be contacted by one of the previously mentioned methods to encourage their

---

continued participation in the study and to ask them to contact the study team concerning their next appointment. Unscheduled visits may occur at the investigator's discretion (Section 6.6).

Participants will be compensated for their participation in the study in an amount stated in the informed consent form, and in some cases, the participant may be eligible for reimbursement of some travel expenses.

## **4.4 Treatment Assignment Procedures**

### **4.4.1 Randomization Procedures**

Prior to randomization, the inclusion and exclusion criteria will be reviewed, and any participant who does not meet the criteria will be discontinued from the trial. Randomization will be stratified across 3 clinical sites for a total of 200 randomized participants. Within each site, participants will be randomized in a 1:1 ratio of active drug to placebo within prespecified blocks. Randomization will be accomplished by a web-based randomization system developed and maintained by the data coordinating center. At the time of randomization, study staff, who will remain blinded to treatment assignment, will access the system, enter the participant's study identification number, and verify that the participant is eligible for randomization. The system will assign a randomization code that will indicate to the pharmacy the participant's treatment assignment.

### **4.4.2 Blinding Procedures**

All study staff, including the study clinicians and investigators, will be blinded to the participants' treatment assignments throughout the data collection period. Propranolol hydrochloride extended-release capsules will be over-encapsulated and cannot be differentiated from the placebo capsules by appearance alone. The research pharmacies will be unblinded. The data coordinating center (DCC) project staff will remain blinded through the analysis for the primary objective. If oversight boards, such as the IRBs or Data and Safety Monitoring Board (DSMB), request an unblinded data report during the data collection period, an unblinded biostatistician at the DCC will generate the report.

### **4.4.3 Unblinding Procedures**

Unblinding before the study is completed will occur only if a participant's well-being is threatened and is necessary to protect the participant. Except in extreme medical emergencies, before the treatment assignment for a participant is unblinded, the investigator must confer with the National Institute of Dental and Craniofacial Research (NIDCR) medical monitor and the site cardiologist as necessary. For extreme medical emergencies that occur during business hours, the clinical site investigator will contact the DCC to determine the participant's treatment assignment. For extreme medical emergencies that occur outside of business hours, medical personnel will contact the site pharmacy to determine the participant's treatment assignment. An event is considered an extreme medical emergency when appropriate medical management of

---

the participant necessitates knowledge of treatment assignment. Study participants will be provided with instructions and contact information for emergency situations. The emergency unblinding will be recorded and reported to the PI and to the NIDCR medical monitor as soon as possible. A full account of the event will be recorded, including the date and time of the emergency, the reason for unblinding, and the names of the medical monitor and others who were notified of the emergency. The unblinding will be reported to the DSMB and the IRBs according to reporting guidelines for those boards.

#### **4.4.4 Reasons for Participant Withdrawal**

Participants are free to withdraw from participation in the study at any time, and the investigator may withdraw a participant for any of the following reasons:

- Withdrawal of consent.
- Does not meet criteria for randomization.
- Pregnancy.
- Continued participation deemed to be not in the participant's best interest.
- Investigator discretion.

Participants requiring significant surgery will be withdrawn from the protocol. Investigators will use discretion in making this determination. Participants withdrawn after randomization will not be replaced. If a participant does not return for a scheduled visit, every effort should be made to contact the participant and document the outcome. If the participant withdraws consent, no further evaluations will be performed, and no attempts will be made to collect additional data.

#### **4.4.5 Handling of Withdrawals and Discontinuation**

Participants who withdraw from the study voluntarily or are withdrawn by an investigator will be discontinued from the study. Study staff will complete a study disposition form in the electronic data capture (EDC) system, indicating the reason for discontinuation. If the participant is on study drug at discontinuation, the investigators, in consultation with the site cardiologist, will decide the following: (1) the need for tapering of the investigational drug, (2) whether tapering will be conducted by the investigator prior to discontinuation or by a referring practitioner after discontinuation, and (3) whether unblinding of the treatment assignment will be required. If unblinding is required, the investigator will follow the unblinding procedures described in Section 4.4.3.

Any participant with an AE that is ongoing at the time of discontinuation will be followed until the event returns to baseline, resolves, or stabilizes. If the AE does not meet these outcomes within 30 days after discontinuation or the end of the study, the participant will be referred to an appropriate practitioner for continued care.

